1 LUCINACTANT FOR INHALATION PROTOCOL 03-CL-1702

1.1 Summary

Protocol Number	03-CL-1702
Title:	A Multinational, Multicenter, Masked, Randomized, Parallel Group, Controlled Study to Assess the Safety and Efficacy of Lucinactant for Inhalation versus nCPAP alone in Preterm Neonates 26 to 32 Weeks Gestational Age with Respiratory Distress Syndrome
Phase:	2b
US IND Number:	119438
ClinicalTrials.gov No.	TBD
EudraCT No.	2018-000106-32
Sponsor:	Windtree Therapeutics, Inc. (Windtree), Warrington, PA, USA
Committees:	Data Monitoring Committee (DMC)
Study Drug and Device:	Lucinactant for inhalation (AEROSURF®, an investigational, drug-device combination product) at 30 mg total phospholipids (TPL)/ml of lucinactant delivered by the AEROSURF Delivery System (ADS) utilizing a capillary-based aerosol generator (CAG).
Active Ingredients:	A 21-amino acid hydrophobic synthetic peptide (sinapultide, KL ₄ peptide), combined with the phospholipids dipalmitoylphosphatidylcholine (DPPC) and palmitoyloleoyl-phosphatidylglycerol, sodium salt (POPG, Na), and the fatty acid palmitic acid (PA).
Rationale:	Respiratory distress syndrome (RDS) of the newborn is a disease that results from insufficiency of pulmonary surfactant in the immature neonatal lung, which carries high morbidity and mortality, especially in very preterm neonates. Exogenous surfactant replacement therapy (SRT) reduces mortality and morbidity and is recommended by multiple

international guidelines. However, SRT requires endotracheal intubation to instill surfactant, often with concomitant positive pressure mechanical ventilation (MV) or insertion of an intratracheal catheter to deliver surfactant (“minimally invasive”). Intubation or insertion of an intratracheal catheter and MV have potentially deleterious effects to the infant and may lead to short- or long-term morbidities.

To avoid endotracheal intubation or intratracheal catheter insertion and MV in preterm neonates with mild to moderate RDS, the use of non-invasive respiratory support with nasal continuous positive airway pressure (nCPAP) has become a widely accepted practice, but SRT cannot be delivered with nCPAP. Although oftentimes successful, nCPAP will fail in approximately one-third to two-thirds of preterm neonates, who generally then require endotracheal intubation, MV, and, in many cases, administration of delayed SRT. Importantly, earlier SRT is more effective than delayed SRT; thus, the inability to administer SRT in conjunction with nCPAP may result in suboptimal timing for SRT to treat RDS.

Therefore, an unmet medical need exists for a means to deliver SRT to preterm neonates with RDS supported with nCPAP early in the course of the disease. This strategy has the potential to prevent progression of RDS that could lead to the development of respiratory failure, and thereby avoid the need for endotracheal intubation and MV, or reduce the duration of MV, and the resultant potential for morbidity and associated complications. The ability to administer SRT non-invasively via an aerosol while infants are on nCPAP support has the potential to address this unmet need.

Windtree Therapeutics, Inc. (Windtree) has developed lucinactant for inhalation (AEROSURF), an investigational drug-device combination product, to deliver aerosolized SRT to preterm neonates with RDS who are being supported with nCPAP. The drug component of lucinactant for inhalation is lyophilized lucinactant, a lyophilized form of SURFAXIN® (lucinactant) Intratracheal Suspension, an exogenous SRT approved by the U.S. Food and Drug Administration (NDA 021746); however, not

currently marketed based solely on business considerations (not as the result of any safety, efficacy, or quality concerns). The device component, the AEROSURF Delivery System (ADS), uses novel technology to aerosolize reconstituted lucinactant.

Three studies of lucinactant for inhalation have been conducted: in preterm neonates 29 to 34 weeks PMA in an open-label safety study (Protocol 03-CL-1201) at escalating theoretical doses of 25, 50, 75, 100 and 150 mg TPL/kg (N=80); in preterm infants 26 to 28 weeks PMA in an open-label safety study (Protocol 03-CL-1401) at escalating theoretical doses of 50, 75, and 100 mg TPL/kg (N=64); and in preterm neonates 28 to 32 weeks PMA in a double-blind safety and efficacy study (Protocol 03-CL-1202) at parallel theoretical doses of 40 mg TPL/kg, 80 mg TPL/kg, and nCPAP only (N=221). In all studies, lucinactant for inhalation was generally well tolerated and there were no safety signals of concern noted with any of the doses. Complications of prematurity, including pulmonary air leak, were comparable between active treatment (lucinactant for inhalation) and control groups (nCPAP alone).

In Studies 03-CL-1201 and 03-CL-1401, exploratory assessment of clinical efficacy suggested that lucinactant for inhalation may be providing beneficial effects. In Study 03-CL-1202, assessment of clinical efficacy noted that fewer subjects in the 80 mg TPL/kg treatment group were intubated for MV or SRT, or met the criteria for respiratory failure, compared to subjects in the nCPAP only group, when lucinactant for inhalation therapy was delivered as intended.

In addition, data from previous studies suggest that a larger initial dose of lucinactant might be needed to improve and maintain pulmonary function; therefore; based on these studies, Windtree will evaluate a lucinactant for inhalation at an initial treatment dose of 160 mg TPL/kg, with up to 3 repeat treatments at 80 mg TPL/kg, versus nCPAP alone. Results from preclinical and clinical trials, including Studies 03-CL-1201, 03-CL-1401, and 03-CL-1202, support the safety and

potential efficacy of this treatment regimen, including the total dose of lucinactant for inhalation to be delivered.

Objectives: To evaluate the safety and efficacy of lucinactant for inhalation delivered by the next generation ADS device in conjunction with nCPAP, in comparison to nCPAP alone, in preterm neonates with RDS, as assessed by the incidence of and time to respiratory failure due to RDS in the first 72 hours and through 28 days of life, oxygen saturation and use of supplemental oxygen, all-cause mortality through 28 days of life, the incidence of bronchopulmonary dysplasia (BPD) at 36 weeks PMA, and the duration of mechanical ventilation. In addition, this study will evaluate the device performance and the ability to administer up to 3 lucinactant for inhalation repeat treatments.

Primary Endpoint: The primary endpoint for this study is the number of subjects with respiratory failure due to RDS or death within the first 28 days of life. Respiratory failure due to RDS is defined as intubation (including intratracheal catheter placement) for MV and/or surfactant administration.

Key Secondary Endpoints: The key secondary endpoints of this study include the evaluation of the following:

- Respiratory failure through 72 hours and 28 days of life
- Time to respiratory failure through 72 hours and 28 days of life
- BPD and survival without BPD at 36 weeks PMA
- Severity of BPD at 36 weeks PMA
- Oxygen saturation and use of supplemental oxygen
- All-cause mortality through 28 days of life and 36 weeks PMA

Other Secondary
Endpoints

Other secondary endpoints of this study include the evaluation of the following:

- Common complications of prematurity through 36 weeks PMA
- Duration of MV and oxygen requirement through 36 weeks PMA
- Changes in fraction of inspired oxygen (FiO₂), partial pressure of carbon dioxide (PCO₂) and oxygen (O₂) saturation, as determined by pulse oximetry (SpO₂) over the first 72 hours of life, and over the first 7 days of life for FiO₂.
- Number and duration of re-hospitalizations and reason for re-hospitalization through 12 months corrected age.
- Respiratory medications through 12 months corrected age.

Study Design:

This study is a multinational, multicenter, double-blind (masked), parallel group, randomized, controlled study to evaluate the safety and efficacy of lucinactant for inhalation in conjunction with nCPAP compared with nCPAP alone, in preterm neonates 26 to 32 completed weeks PMA who are being cared for in a neonatal intensive care unit (NICU), who had successful implementation of non-invasive respiratory support or ventilation within 30 minutes of birth, and who are candidates for SRT. It is strongly recommended that the initial mode of support is study nCPAP (bubble nCPAP); however, other non-invasive modes are acceptable if the investigator feels it is safe to switch the subject to study nCPAP following consent and screening. There will be 2 phases in the study, a primary phase through 36 weeks PMA or 28 days of life (whichever is longer), and a longer-term follow-up phase through 12 months corrected age. Data will be analyzed and reported at the completion of each respective study phase.

Before study enrollment, legally authorized representatives will provide a signed informed consent form (ICF) for each potential subject; it is recommended that informed consent be obtained antenatally. Qualification for study enrollment will be established after confirmation that the subject has met all of the inclusion criteria and none of the exclusion criteria. The clinical criteria for enrollment may be met prior to

informed consent being obtained; however, no study-specific procedures that are not part of the required care of the subject at the institution may be performed until the informed consent has been provided by a legally authorized representative of the subject. Time to treatment is potentially an important factor in the success of non-invasive delivery of surfactant. Because of this and other operational factors, antenatal consent should be obtained where permitted.

Inclusion criteria to be met within the first 6 hours after birth include respiratory insufficiency with a requirement for nCPAP of 5 to 7 cm H₂O and an FiO₂ > 0.25 to ≤ 0.35, to maintain SpO₂ of 90% to 95% for at least 15 minutes. As soon as study qualification has been confirmed and the informed consent is signed, subjects will be randomized to an active treatment group or to the control group (nCPAP only, with simulated [“sham”] study drug treatment). Study treatment (160 mg TPL/kg lucinactant for inhalation or sham/control) must be initiated as soon as possible (within 2 hours of randomization), but no more than 8 hours after birth. Neonates who are randomized and on study nCPAP but no longer meet qualification criteria before treatment will still receive the study treatment, unless it is unsafe to do so in the opinion of the investigator. In order to ensure correct functioning of the ADS and reinforce study treatment procedures, the first 2 subjects at each site will be dosed open-label on active study treatment (initial dose of 160 mg TPL/kg lucinactant for inhalation). All procedures for treatments and repeat treatments are exactly the same.

Subsequent to the initial dose of 160 mg/kg lucinactant for inhalation or sham, subjects are eligible to receive up to 3 repeat study treatments (a total of 4 study treatments) of active or sham to which they are originally assigned; however, the dose of the active treatment will be 80 mg TPL/kg. Repeat treatments will be given as soon as 20 minutes from completion of the previous treatment up to 36 hours after randomization if the subject meets repeat treatment criteria (as described in the “Treatment Groups” section). If the subject is not on room air (FiO₂ = 0.21) at the conclusion of any active or sham study treatment

dosing (eg, 50 minutes after treatment initiation), the subject should receive a repeat treatment as soon as possible after the end of treatment (but \geq 20 minutes), unless to do so would present a risk to the subject in the opinion of the principal investigator (PI). Subjects randomized to the control group will be continued on nCPAP alone but will receive repeated sham treatments to maintain study masking. The PI will follow routine practice guidelines to determine when a subject in either treatment group requires escalation of respiratory support including endotracheal intubation or rescue surfactant therapy.

Subjects in the active treatment group will receive lucinactant for inhalation at a concentration of 30 mg TPL/ml, at a rate of delivery of approximately 4.2 mg TPL/L in aerosol carrier gas flow of 3 L/min. The delivered dose of 160 mg TPL/kg (80 mg TPL/kg for repeat treatments) is based on the predetermined administration time of approximately 100 minutes of aerosol delivery (50 minutes for repeat treatments). Reconstituted lucinactant will be delivered by the investigational ADS device in conjunction with a commercially available nCPAP generator and patient interface. Treatment assignments will be masked from the PI and applicable study staff, bedside care team, sponsor (as applicable), and subject's legally authorized representative.

All enrolled subjects will receive study treatment in a NICU: a specialized care center staffed by neonatologists, nurses, and respiratory therapists who are experienced in the delivery of emergent care to the preterm neonatal population. Neonates in the NICU are continuously monitored using advanced and sophisticated monitoring equipment, and there is ready and immediate access to equipment, medications, and skilled personnel that may be needed to address emergent developments. Interventions such as endotracheal intubation, MV, and surfactant administration will be readily available to all study subjects if clinically indicated in accordance with the high-level standard-of-care customary in the NICU.

Neonates will be followed for the primary phase through 36 weeks PMA (or 28 days of life, whichever is later), hospital discharge, hospital

transfer, or death (whichever occurs first). For the longer-term follow-up phase, neonates will be evaluated by phone at 6-months corrected age and a visit at 12-months corrected age. Assessments during the longer-term follow-up include number of days on respiratory support, hospitalization information, overall health assessment, an abbreviated physical examination, and an abbreviated neurologic assessment.

Study Population: The study population will be comprised of preterm neonates 26 to 32 completed weeks PMA who are spontaneously breathing and receiving care in a NICU and are receiving bubble nCPAP as the primary support modality for RDS. Enrollment will be conducted by strata: 26 to 28 completed weeks PMA and 29 to 32 completed weeks PMA. In order to evaluate strata, each stratum will enroll a minimum of 7 subjects per arm (approximately 20% of total).

The study population will be randomized in a 1:1 ratio into 1 of 2 treatment groups (see “Treatment Groups” section).

Study Sample Size: A total of up to 130 study subjects (approximately 50% in each treatment group) will be enrolled.

Number of Sites: Approximately 20 study sites in North America, Europe, Asia, and/or Latin America.

Study Duration: Overall, study enrollment will be completed in approximately 8 to 9 months, with the last subject reaching 36 weeks PMA approximately 10 months from the time the first subject enrolled.

For the primary phase of the study, subject participation will be from ≤ 6 hours following birth until 36 weeks PMA (or 28 days of life, whichever is later), hospital discharge or transfer, or death, whichever occurs first. Follow-up through 12-months corrected age will be done for the secondary phase of the study.

Method of Administration: Subjects randomized to the active treatment groups will be administered an investigational drug-device combination product, lucinactant for inhalation, in conjunction with nCPAP. Reconstituted lyophilized lucinactant (reconstituted with sterile water for injection) will be aerosolized by the investigational ADS device and introduced into the nCPAP circuit. Those randomized to the control (nCPAP only) group will receive nCPAP alone. In order to maintain treatment masking, “sham” study treatment will be used: the ADS will be brought to the bedside, appropriate visual shielding will be employed, but the ADS will not be used and no study drug will be administered.

The theoretical inhaled dose (in mg TPL/kg) can be controlled based on the duration of exposure to the aerosol. This inhaled dose is a function of the concentration of lucinactant in the aerosol, the amount of aerosol inhaled by the subject (estimated by the subject’s minute ventilation, assuming that all gas inhaled by the subject contains the same concentration of aerosol), and the duration of exposure to the aerosol.

Treatment Groups: **160 mg/kg** 160 mg TPL/kg of lucinactant for inhalation, delivered as two consecutive 50-minute administrations, in conjunction with nCPAP (N ≈ 65).

Up to 3 repeat study treatments of 80 mg TPL/kg administered over 50 minutes will be given if repeat treatment criteria are met.

Control Continuous nCPAP (N ≈ 65) as sham study treatment for 110 minutes.

Up to 3 repeat sham study treatments (50 minutes) will be given if repeat treatment criteria are met.

The first 2 subjects at each site will be dosed open-label with active study treatment. Both open-label and masked subjects randomized to lucinactant for inhalation will be dosed with the same dosing regime (initial dose of 160 mg TPL/kg followed by 80 mg TPL/kg for repeat treatments).

Repeat treatments (active or sham) will be given ≥ 20 minutes from completion of the previous treatment up to 36 hours after randomization if subjects have a need for FiO_2 above room air (ie, $\text{FiO}_2 > 0.21$), unless it is unsafe to do so in the judgment of the PI. Masking procedures for the initial study treatment will be followed for repeat treatments, including controls.

Inclusion Criteria: Each subject must meet all inclusion criteria to be enrolled in this study:

1. Signed ICF from legally authorized representative. It is recommended that consent is obtained antenatally (where permitted).
2. Gestational age: $26^{0/7}$ to $32^{6/7}$ weeks PMA.
3. Successful implementation of non-invasive ventilation within 30 minutes after birth.
4. Spontaneous breathing.
5. Investigator determination of RDS. A chest x-ray must be obtained before treatment to confirm the diagnosis.
6. Within the first 6 hours after birth, requires an nCPAP of 5 to 7 cm H₂O that is clinically indicated for at least 15 minutes with an $\text{FiO}_2 > 0.25$ to ≤ 0.35 to maintain SpO₂ of 90% to 95%. Transient (<5 minutes) FiO_2 excursions outside this range do not reset the time requirement.

Exclusion Criteria: Subjects meeting any exclusion criteria must not be enrolled in this study:

1. A heart rate that cannot be stabilized above 100 beats per minute (bpm) within 5 minutes of birth.
2. Recurrent episodes of apnea requiring positive pressure ventilation (PPV) administered manually or mechanically through any patient interface.
3. A 5-minute Apgar score < 5.
4. Major congenital malformation(s) or craniofacial abnormalities that preclude the use of nCPAP, diagnosed antenatally or immediately after birth.
5. Clinically significant diseases or conditions other than RDS which could potentially interfere with cardiopulmonary function (eg, congenital heart disease, hydrops fetalis or congenital infection).
6. A known or suspected chromosomal abnormality or syndrome.
7. Premature rupture of membranes > 3 weeks.

8. Hemodynamic instability requiring vasopressors or steroids for hemodynamic support and/or presumed clinical sepsis.
9. A need for intubation and/or invasive mechanical ventilation at any time before enrollment into the study.
10. The administration (or plan for administration) of any the following:
 - a) Another investigational agent or investigational medical device
 - b) Any other surfactant agent
 - c) Systemic corticosteroids (other than antenatal steroids)
11. Presence of air leak (pneumothorax, pneumomediastinum, pneumopericardium, subcutaneous emphysema, or definite evidence of pulmonary interstitial emphysema [PIE]) on the baseline chest radiograph or diagnosed via ultrasound or illumination.

Concomitant Medications:

All concomitant medications administered to the subject from birth until 36 weeks PMA, hospital discharge, hospital transfer, or death (whichever occurs first) will be recorded in the electronic case report form (eCRF).

Medications required for the general care of the subject are permitted with the exception of investigational agents, investigational medical devices, or any SRT before randomization. Commercially available SRTs, following study treatment, may be administered as medically indicated (ie, “rescue surfactant”). Study subjects who receive any commercial SRT while on-study will be considered treatment failures but will continue to be followed until study completion. Postnatal steroids are not permitted unless clear medical need is determined. Use of caffeine citrate or other methylxanthines is recommended.

Safety and Tolerability Endpoints:

The safety and tolerability endpoints will be assessed during the primary phase through 36 weeks PMA, hospital discharge, hospital transfer, or death, whichever occurs first, as described below.

1. All-cause mortality through 28 days of life and 36 weeks PMA
2. AEs, including adverse device effects (ADEs). SAEs that are ongoing at 36 weeks PMA will be followed for an additional 30 days
3. Concomitant medications

4. Use of any type of respiratory support (invasive or non-invasive), including an oxygen requirement ($\text{FiO}_2 > 0.21$) or the need for endotracheal intubation and MV
5. Complications of prematurity, including air leak
6. Physical examinations
7. Assessments of the following:
 - a. Vital signs
 - b. FiO_2
 - c. SpO_2
 - d. CPAP/PEEP
 - e. Chest radiography prior to intubation

Early
Discontinuation of
Treatment:

The administration of study treatment may be discontinued at any time prior to the completion of dosing if certain device malfunctions or interruptions occur which cannot be corrected in a safe and timely manner or based on the clinical judgment of the PI. Reasons for discontinuation of study treatment include, but are not limited to the following:

1. A device malfunction occurs
2. The device shuts down as a result of a detected out of range condition
3. An AE or ADE which places subject at risk occurs (eg, pulmonary hemorrhage; airway obstruction)
4. If, in the PI's best medical judgment, initiating or continuing the subject's exposure to study treatment is not in the best interest of the subject's safety
5. Signs of acute respiratory deterioration develop, as evidenced by a clinically significant increase in respiratory rate or effort (work of breathing) plus at least one of the following:
 - a) A persistent (at least 10 minutes) $\text{FiO}_2 \geq 0.70$ or sustained increase from baseline by ≥ 0.30 to maintain SpO_2 90% to 95%
 - b) A persistent (at least 5 minutes) transcutaneous $\text{PCO}_2 > 70 \text{ mmHg}$ or an increase from baseline by $\geq 20 \text{ mmHg}$
 - c) Recurring episodes of bradycardia
 - d) A sustained apneic event (≥ 20 seconds)

Subjects whose treatment is discontinued based on the PI's judgment will continue in the study. Subjects whose treatment is discontinued based on the parent/guardian's withdrawal of consent will be withdrawn from the study and no further data collection will be done.

Statistical Analysis The statistical analysis of objectives will be based on all enrolled preterm neonates. The subjects enrolled open-label with active treatment (the first 2 subjects from each site) will be summarized separately; however, AEs and other safety information may also be pooled with data from the double-blind portion of the study.

For the efficacy analysis, populations of all randomized subjects who received any treatment (modified intent-to-treat [mITT]) and subjects with no major protocol deviations or treatment interruptions (per-protocol) will be evaluated, based upon the treatment group to which they were randomized. For the safety analysis, all subjects randomized to the control group or who received any lucinactant for inhalation (including partial doses) will be evaluated, based upon the treatment they actually received.

The primary efficacy analysis will be performed using logistic regression. Secondary and tertiary endpoints will be assessed using either Cochran-Mantel-Haenszel or log-rank tests.

Interim Analyses: During the primary phase, the chair of the data monitoring committee (DMC) will receive regular reports (eg, bi-weekly) on SAEs and AEs of interest. There will be one planned meeting when enrollment is approximately 1/3 of total; ad hoc meetings of the DMC will occur if deemed necessary to address safety in the study.

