Subjects may be eligible to receive up to 3 repeat study treatments (active or sham) to which they are assigned; however, the dose of the active treatment will be 80 mg TPL/kg. Repeat treatments will be given as soon as 20 minutes from completion of the previous treatment up to 36 hours after randomization if subject meets repeat treatment criteria, unless it is unsafe to do so in the judgment of the PI, as described in Section 6.6. Subjects randomized to the control group will be continued on nCPAP alone but will receive repeated sham treatment to maintain study masking. Details on the ADS is outlined in Section 6.1.

[figure not shown]
Treatment assignments, outside the first 2 open-label subjects who will receive active study treatment, will be masked from the PI; clinical and study staff (eg, site coordinator, bedside nurse), as applicable; sponsor, as applicable; and subject's parents/legal guardians. All enrolled subjects will receive study treatment in a NICU, a specialized care center staffed by neonatologists, nurses, and respiratory therapists who are experienced in the delivery of emergent care to the preterm neonatal population. Neonates in the NICU are continuously monitored using advanced and sophisticated monitoring equipment, and there is ready and immediate access to equipment, medications, and skilled personnel that may be needed to address emergent developments. Interventions such as endotracheal intubation, MV, and traditional surfactant administration will be readily available to all study subjects if clinically indicated in accordance with the high-level standard-of-care customary in the NICU.

Neonates will be followed for the primary phase efficacy and safety evaluations through 36 weeks PMA, hospital discharge, hospital transfer, or death (whichever occurs first). For the longer-term follow-up phase, neonates will be evaluated by phone at 6-months corrected age and at a visit at

12-months corrected age, at which time a physical examination will be performed, including an abbreviated neurologic assessment. (See also Section 8.)

A schematic diagram of the study design is displayed in Figure 3-1.

Figure 3-1. Schematic of Study Design for 03-CL-1702

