13.2 Statistical and Analytical Plans

The statistical analysis of both the primary and secondary objectives will be based on all enrolled preterm neonates who received study therapy. The first 2 subjects at each site, which were treated with open-label active therapy will be summarized separately. However, the safety data from these subjects may be pooled with the safety data from the subjects that received blinded therapy. The efficacy data will not be pooled.

For the efficacy analysis, all randomized subjects who received study therapy (modified intent-to-treat [mITT]) and subjects with no major protocol deviations (per-protocol) will be evaluated, based upon the treatment group to which they were randomized. If necessary, a population of subjects without treatment interruptions will also be defined and analyzed. For the safety analysis, all control subjects and subjects who received any amount of aerosolized lucinactant will be evaluated, based upon the treatment they actually received. All analyses will be performed for all subjects combined by treatment group and by gestational age strata.

All continuous variables (eg, weight, body temperature) will be summarized using number (n), mean, standard deviation (SD), median, 1st quartile, 3rd quartile, minimum, and maximum. All discrete variables (eg, sex, AEs, common complications of prematurity), will be summarized using frequency (n) and percent. Sites will be pooled for statistical analyses by geographic region.

The primary endpoint (the incidence of respiratory failure due to RDS or death within 28 days of life) is defined in Section 4.3.1. Respiratory failure due to RDS is defined as intubation (including intratracheal catheter placement) for MV and/or surfactant administration and will be compared between active treatment and control using the Cochran-Mantel-Haenszel (CMH) test, controlling for pooled sites.

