4.1 Efficacy Populations

For efficacy analyses, subjects will be summarized according to their assigned (randomized) treatment. The subjects enrolled open-label with active treatment (the first 2 subjects from each site) will not be summarized separately.

The analysis of both the primary and secondary objectives will be based on all enrolled preterm neonates (ITT population).

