6 SAFETY ANALYSES

6.1 Safety Population

The safety population is defined as all subjects who received any study medication, active or sham. Subjects will be included in the treatment group for the treatment actually received (if different than the group that they were randomized). The subjects enrolled open-label with active treatment (the first 2 subjects from each site) will be pooled with data from double-blind portion of the study. All safety assessments will be based on this population.

Safety analyses will be summarized by all subjects combined and by country or region.

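### SAP 6.1 pools the open-label active infants into the active safety column, without the separate summary that the Protocol requires

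*Protocol*

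**What the plan says.** Both documents give the first two infants at each site open-label active treatment, and only later infants are allocated between the masked groups. The Protocol gives the reason in 1.1 and 3.1: to check that the device works and to reinforce the treatment procedures. On masking, Protocol 3.1 states that assignments "outside the first 2 open-label subjects who will receive active study treatment, will be masked from the PI".

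The Protocol handles these infants cautiously. Section 1.1 says that those enrolled open-label ("the first 2 subjects from each site) will be summarized separately", and continues that "AEs and other safety information may also be pooled with data from the double-blind portion of the study". Section 13.2 follows the same order: a separate summary first, after which "the safety data from these subjects may be pooled with the safety data from the subjects that received blinded therapy". For efficacy it is strict: "The efficacy data will not be pooled".

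The SAP, dated after enrolment had stopped at 12 infants, is different. Section 6.1 says the open-label infants "will be pooled with data from double-blind portion of the study" and adds: "All safety assessments will be based on this population". The Executive Summary leaves one analysed population, called ITT for efficacy and safety for safety. The list in SAP Section 11 assigns Tables 6.1 to 7.4 to the safety population and names no table for masked randomised infants or for open-label infants. For efficacy, SAP 4.1 explicitly withdraws the separate summary ("the first 2 subjects from each site) will not be summarized separately").

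**The concern.** An open-label infant can add to the active column only, because no control infant is enrolled this way. After pooling, the control column is still randomised and masked, while the active column is a mixture. Its open-label part differs in three respects:

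- **Allocation.** Active drug is given by order of enrolment, outside the 1:1 allocation within gestational-age stratum. Protocol 6.5 and SAP 8.1 pass these infants through the central system, but with only one possible assignment that is registration, not randomisation.
- **Site experience.** They are each site's first uses of the device in this study, so peri-dosing events and device effects are open to any learning effect.
- **Ascertainment.** The PI is not masked for them. Under Protocol 9.1.2 the PI grades severity, and under 9.1.1 the PI or a blinded designee judges relatedness.

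A difference between the columns, or the lack of one, could then reflect reporting, learning or case mix instead of the drug. It could hide a harm or suggest one. The exposure is greatest for investigator-judged outcomes (severity, relatedness, peri-dosing events) and least for deaths.

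**Working it through.** The plan states no figure for the open-label share, so there is none to reproduce. The only related figure is the planned split: 130 × 0.5 = 65 per group.

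**Inputs**
- Open-label infants: 2 per site, all active (Protocol 1.1).
- Planned total: up to 130 (Protocol 1.1 and 13.4).
- Planned sites: about 20 (Protocol 1.1) or about 10 (SAP 2.1).
- Enrolled: 12 infants, in Poland (SAP 2.1). The number of sites is not given.

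**Formula.** Let w be the open-label share of the pooled active column, and D the open-label event rate minus the masked active event rate. The pooled active rate is (masked active rate) + w × D. Pooling therefore moves the active-minus-control difference by w × D, up or down with the sign of D.

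**The 12 infants enrolled.** With s sites, two open-label infants at each and the rest split evenly, there are 2s open-label infants, (12 − 2s)/2 = 6 − s controls, and 2s + (6 − s) = 6 + s active infants. So w = 2s/(6 + s).

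| Sites (assumed) | Open-label / all active | w | Masked active | Control |
|---|---|---|---|---|
| 1 | 2 / 7 | 29% | 5 | 5 |
| 2 | 4 / 8 | 50% | 4 | 4 |
| 3 | 6 / 9 | 67% | 3 | 3 |
| 4 | 8 / 10 | 80% | 2 | 2 |

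Five sites would give 10 of 11. Six would leave no randomised infant at all.

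**The full planned trial, had the Protocol's pooling option been used.** The documents do not say whether the open-label infants count towards the 130, so both readings are shown.

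| Sites | Open-label | Outside the 130 | Inside the 130 |
|---|---|---|---|
| 10 | 20 | 20/(65 + 20) = 23.5% | (130 − 20)/2 = 55 per arm; 20/75 = 26.7% |
| 20 | 40 | 40/(65 + 40) = 38.1% | (130 − 40)/2 = 45 per arm; 40/85 = 47.1% |

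For D = 10 points, the difference shifts by 2.4 to 2.7 points at 10 sites and by 3.8 to 4.7 points at 20 sites. D itself is unknown, and the documents give no estimate of it.

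**Does ascertainment matter in this programme?** In the open-label Study 03-CL-1201 (Protocol 2.3.2.1), investigators reported air leak in 9 of 40 active and 7 of 40 control infants (23% v 18%). Independent radiograph review confirmed the 9 and found 2 more in controls, giving 23% in both groups. Two infants prove no bias, but they show that investigator reports can change an apparent difference between arms. In the present study a blinded radiograph review is only optional (Protocol 8.3).

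**The case against.** The case on the other side has real force.

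- **The Protocol is not at fault.** Its pooling is optional and comes on top of a required separate summary. A reader who stops at the pooling clause might infer that the Protocol itself replaces the randomised display, and the rest of the text does not support that. The definite rule is in SAP 6.1.
- **No AE test is affected.** Protocol 13.2 says AEs will not be compared statistically, SAP 6.3 says TEAEs will not be compared between groups, and SAP 8.3 excludes all testing. Protocol 13.2 did plan Cochran-Mantel-Haenszel tests for mortality and for complications of prematurity, chiefly air leak. All-cause mortality is a key secondary efficacy endpoint there, so the rule against pooling efficacy data covers its test, and arguably the air-leak test too.
- **An as-treated set of all exposed infants is a normal safety population,** and the open-label infants share the eligibility criteria and regimen.
- **Some outcomes are robust.** Unmasked reporting hardly touches deaths. Air leak is defined on radiographs. SAEs and deaths are also listed individually.
- **Twelve infants support no AE contrast,** pooled or not.

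All of this limits the weight of the point, but it does not remove it. Safety is still tabulated by treatment group, readers will set the columns side by side, and the SAP provides no masked-only display to turn to. Rehearsing the blinding procedures for the open-label infants (Protocol Section 6) does not conceal a treatment that is fixed in advance. Including every exposed infant is compatible with showing the two sources apart.

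**Conclusion.** The point holds as a gap in the SAP. Section 6.1 makes pooling definite for all safety assessments and, with the table list, leaves out the separate summary that Protocol 1.1 and 13.2 require. The by-treatment safety summaries are then not a masked randomised display. The result is potential descriptive bias of unknown direction, concentrated in investigator-judged outcomes.

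For the 12 infants, the open-label share of the active column is 29% to 80% at one to four sites, assuming two open-label infants at every site and an even split of the rest. The true value depends on a site count that the documents do not give.

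Two stronger readings are not supported. A reader might infer that 38% to 47% of the active safety column was bound to be open-label. That range needs the Protocol's 20 sites, where pooling was only optional. The mandatory rule appears only in a SAP written after enrolment ended, and the SAP's own 10 sites would give 24% to 27%. A reader might also infer that the safety results are shown to be biased or that a test is invalid. The documents give no estimate of how open-label and masked rates differ, and they plan no AE test.

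**What to change.** In SAP 6.1 and in safety Tables 6.1 to 7.4, show masked active, masked control and open-label active in separate columns. Add the open-label infants to the masked active infants only in a total-exposed column, labelled non-randomised and not set against control. In Protocol 1.1 and 13.2, state that any pooled safety summary is additional to this layout.

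The cost is SAP wording and one or two extra table columns, some with very small counts. No new data are needed, no exposure information is lost, and the Protocol's separate summary is restored. With enrolment closed, reporting is the only stage at which this can still be done.
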